10.2 APPENDIX 2: CLINICAL LABORATORY TESTS

- The tests detailed in [Table 18](#) will be performed by the local laboratory.
- Protocol-specific requirements for inclusion or exclusion of participants are detailed in [Section 5](#) of the protocol.
- Additional tests may be performed at any time during the study as determined necessary by the Investigator or required by local regulations.

- Pregnancy testing will be performed in all WOCBP at baseline, at End of treatment visit, and the 3 month follow-up, as detailed in the SOA ([Section 1.3](#)). Women of child-bearing potential must have a negative serum pregnancy test result within 7 days prior to the initial intervention; at the End of treatment evaluation (30 ± 5 days after the last IMP administration); and at the Follow-up (90 ± 7 days after the last IMP administration). Additionally, during the treatment period, serum/urine pregnancy tests will be performed at the beginning of the visit every 4 weeks (ie, every 2 cycles/every other cycle).

Table 18 - Protocol-required safety laboratory assessments

Laboratory assessments	Parameters
Hematology	Platelet count Red blood cell (RBC) count Hemoglobin Hematocrit White blood cell (WBC) count with differential: Neutrophils Lymphocytes Monocytes Eosinophils Basophils
Clinical blood chemistry ^a	Urea/blood urea nitrogen (BUN) Creatinine Glucose Potassium Sodium Calcium Aspartate aminotransferase (AST)/ Serum glutamic-oxaloacetic transaminase (SGOT) Alanine aminotransferase (ALT)/ Serum glutamic-pyruvic transaminase (SGPT) Alkaline phosphatase Total and conjugated bilirubin Total protein Albumin LDH Coagulation parameters (INR, aPTT)
Thyroid function (triplet cohort only)	Thyroid-stimulating hormone (TSH) Total tri-iodothyronine (T3) Free thyroxine (FT4)
Serum/urine pregnancy ^b	

NOTES :

a Details of liver chemistry stopping criteria and required actions and follow-up assessments after liver stopping or monitoring event are given in Section 8.2.6.5. All events of Grade 4 AST/ALT increase must be reported as an SAE. Investigators must document their review of each laboratory safety report.

b Only for WOCBP.

10.3 APPENDIX 3: ADVERSE EVENTS: DEFINITIONS AND PROCEDURES FOR RECORDING, EVALUATING, FOLLOW-UP, AND REPORTING

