- c D1 pre-dose: Cycle 1 D1 refers to the day the participant receives the initial dose of IMP. D1 of Cycle 2 and of each subsequent cycle corresponds to D15 of the previous cycle. During treatment, D1 assessment can be done on the day of infusion (before infusion) or the day before. C1D1 hematology, blood chemistry, coagulation and urinalysis tests may be omitted if baseline test performed within 7 days are normal. If baseline tests are abnormal should be repeated within 2 days of first study intervention.
- d Follow-up visit: SAEs (regardless of relationship with study treatment) and IMP-related AEs ongoing at the end of study treatment, and any new IMP-related AE/SAE/AESI will be followed until resolution or stabilization (defined as an event ongoing without any change for at least 3 months). Date of disease progression and further anticancer treatment will be collected at the follow-up visit. Participants who stopped treatment before documented progressive disease (PD; ie, achieving stable disease [SD], or complete or partial response [CR or PR]) should undergo a tumor assessment and an on-site follow-up visit every 12 weeks (± 7 days) after the last tumor assessment until radiological disease progression, death, study cut-off date of the secondary ORR endpoint of the triplet cohort, initiation of further anti-cancer therapy, or withdrawal of participant's consent, whichever comes first. Participants with documented disease progression should attend an on-site follow-up visit 90 days after the last dose of study medication. If every ongoing related AE/SAE/AESI is resolved or stabilized, no further follow-up visit is needed.
- e Disease history includes previous antitumor therapy (type, start and end dates, reason for discontinuation and response to the therapy) and smoking history.
- f NSCLC characteristics will include histologic types, stage at diagnosis, disease extent at study entry, (collected at screening) and specific mutations including PD-1 expression status (to be collected only at prescreening).
- g Physical examination will include: vital signs (temperature, blood pressure, heart rate) and examination of major body systems. Signs and symptoms will be reported in the electronic case report form (eCRF) as AEs only if they are still present at the time of first IMP administration

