1.3.2 Study flow chart - Triplet cohort

Procedure	Pre-screening ^a	Screening ^b	Treatment cycle 1		Treatment cycle 2 +		End of treatment	90 (± 7) Days (3 month) Follow-up ^d	Notes*
Day		Days to first infusion	D1		21 (± 3) days from previous infusion		30 (± 5) days from last infusion		
			Pre-infusion ^c	EOI	Pre-infusion ^c	Every 6 weeks (± 7 days)			
CEACAM5 expression status ^a (archival or fresh tumor tissue) – central IHC/ prescreening Informed consent	X								
Informed Consent		X							
Inclusion/exclusion criteria		≤ 28	X						Section 5.1, 5.2
Demography, medical/surgical/disease/smoking history ^e		≤ 28							
NSCLC characteristics ^f	X	≤ 28							
Height		≤ 7							
Performance status (ECOG)		≤ 7	X		X		X	X	Section 8.2.1, 8.2.3
Physical examination, including vital signs, body weight ^g		≤ 7	X		X		X	X	Section 8.2.1
Hematology ^h		≤ 7	X		X		X		Section 8.2.5, 10.2 (Appendix 2)
Coagulation ⁱ		≤ 7	X		X		X		Section 10.2 , (Appendix 2)
Clinical blood chemistry ^j		≤ 7	X		X		X		Section 8.2.5, 10.2 (Appendix 2)
Thyroid function		≤ 7			X		X		
Urinalysis ^k		≤ 7	X		X				Section 10.2 , (Appendix 2)
HBsAg & HCV serology and HIV test (only if required at country level)		X							Section 10.8 , (Appendix 8)

Procedure	Pre-screening ^a	Screening ^b	Treatment cycle 1		Treatment cycle 2 +		End of treatment	90 (± 7) Days (3 month) Follow-up ^d	Notes*
Day		Days to first infusion	D1		21 (± 3) days from previous infusion		30 (± 5) days from last infusion		
			Pre-infusion ^c	EOI	Pre-infusion ^c	Every 6 weeks (± 7 days)			
Urine or Serum pregnancy test ^l		≤ 7			X		X	X	Section 10.2 (Appendix 2) Section 10.5 (Appendix 5)
Left ventricular ejection fraction (MUGA/echocardiogram) ^m		≤ 28							Section 8.2.4.2
12-lead ECG ⁿ		≤ 7	X	X	X		X		Section 8.2.4.1
Specific ocular tests ^o		≤ 28					X		Section 8.2.2
Tusamitamab ravtansine/Ramucirumab/Pembrolizumab administration			X		X				Section 6.1
AE assessment ^p	X		Continuously throughout the study period						Section 8.2, 8.3, 10.3 (Appendix 3)
Concomitant medication ^q		X	Continuously throughout the study period						Section 6.5
Tumor assessment – RECIST v1.1 - CT/MRI; relevant surrogate markers ^r		≤ 28				X	X	X	Section 8.1
Circulating CEA ^s	X	≤ 28				X	X	X	
IgG			X						
Record further anticancer therapy								X	
Tusamitamab ravtansine PK			Refer to PK/ATA flowchart, Section 1.3.3						Section 8.5
Tusamitamab ravtansine Immunogenicity			Refer to PK/ATA flowchart, Section 1.3.3						Section 8.9

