- c D1 pre-dose: Cycle 1 D1 refers to the day the participant receives the initial dose of IMP. D1 of Cycle 2 and of each subsequent cycle corresponds to D22 of the previous cycle. During treatment, D1 assessment can be done on the day of infusion (before infusion) or the day before. C1D1 hematology, blood chemistry, coagulation and urinalysis tests may be omitted if baseline test performed within 7 days are normal. If baseline tests are abnormal should be repeated within 2 days of first study intervention.
- d Follow-up visit: SAEs (regardless of relationship with study treatment) and IMP-related AEs ongoing at the end of study treatment, and any new IMP-related AE/SAE/AESI will be followed until resolution or stabilization (defined as an event ongoing without any change for at least 3 months). Date of disease progression and further anticancer treatment will be collected at the follow-up visit. Participants with documented disease progression should attend an on-site follow-up visit 90 days after the last dose of study medication. If every ongoing related AE/SAE/AESI is resolved or stabilized, no further follow-up visit is needed.
- e Disease history includes previous antitumor therapy (type, start and end dates, reason for discontinuation and response to the therapy) and smoking history.
- f NSCLC characteristics will include histologic types, stage at diagnosis, disease extent at study entry, (collected at screening) and specific mutations including PD-1 expression status (to be collected only at prescreening).
- g Physical examination will include: vital signs (temperature, blood pressure, heart rate) and examination of major body systems. Signs and symptoms will be reported in the electronic case report form (eCRF) as AEs only if they are still present at the time of first IMP administration
- h Hematology: Hemoglobin, hematocrit, RBC, WBC with differential, platelet counts. These tests will be done before IMP administration at each cycle. If Grade 4 neutropenia, assess absolute neutrophil count (ANC) every 2-3 days until ANC $\geq 0.5 \times 10^9/L$. During first cycle, hematology will be performed weekly.
- i Coagulation: International normalized ratio (INR), aPTT.

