- j Clinical blood chemistry: Liver function tests: SGOT (AST), SGPT (ALT), total bilirubin, conjugated bilirubin, AP. Renal function tests: Urea (or BUN) & creatinine. Electrolytes: Sodium, potassium, calcium, glucose. Others: LDH, albumin and total proteins. During first cycle, liver function tests will be performed weekly. The liver function tests and renal function tests will be done before IMP administration at each cycle, unless clinically appropriate. In case of Grade ≥ 3 liver function abnormal tests, additional tests will be repeated every 2-3 days until recovery to baseline value.
- k Urinalysis tests on morning spot will be performed by dipstick at baseline, and at every treatment cycle. In case of proteinuria $\geq ++$ (dipstick), proteinuria quantification by proteinuria/24 h should be performed.
- l Serum pregnancy test: women of childbearing potential must have a negative serum pregnancy test result within 7 days prior to the initial dose of IMP. A pregnancy test (serum/urine) will be repeated every 4 weeks before IMP administration, and a serum test will be repeated at the End of Treatment evaluation (30 \pm 5 days after the last IMP administration), and at the Follow-up visit (90 \pm 7 days after last IMP dose).
- m Echocardiogram or MUGA scan: left ventricular ejection fraction (LVEF) will be evaluated during screening period, and whenever clinically indicated.
- n 12-lead ECG is required at baseline (In case the ECG performed less than 7 days before 1st IMP administration is considered as normal, there is no need to repeat it just before the 1st IMP) before starting and after completing the first IMP administration (within 30 minutes after the end of tusamitamab ravtansine infusion); before IMP administration at each cycle; and at the End of treatment evaluation, 22 to 30 days after last IMP administration.
- o Specific ocular tests will include assessment of ocular/visual symptoms and ocular exams including visual acuity, slit lamp under dilatation, and Schirmer's test at screening and whenever clinically indicated.
- p AE: For participant who was prescreened and had fresh biopsy, only the Adverse Events related to the fresh biopsy procedure itself should also be reported in eCRF as general requirement of AE/SAE with the reporting time frame interval of 1 month for the prescreening period after fresh biopsy.

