8 STUDY ASSESSMENTS AND PROCEDURES

- Study procedures and their timing are summarized in the SOA ([Section 1.3](#)). Protocol waivers or exemptions are not allowed. For a regional or national emergency declared by a governmental agency, contingency measures are included in Appendix 11 ([Section 10.11](#)).
- Adherence to the study design requirements, including those specified in the SOA, is essential and required for study conduct.
- All screening evaluations must be completed and reviewed to confirm that potential participants meet all eligibility criteria. The Investigator will maintain a screening log to record details of all participants screened and to confirm eligibility or record reasons for screening failure, as applicable.
- Procedures conducted as part of the participant's routine clinical management (eg, blood count) and obtained before signing of the ICF may be utilized for screening or baseline purposes provided the procedures met the protocol-specified criteria and were performed within the time frame defined in the SOA.
- In patients who failed prescreening, limited information will be collected as detailed in [Section 1.3](#).

During the screening period, demography, medical/surgical and disease history will be evaluated. Demography includes age, gender, race, and ethnicity. Medical/surgical history includes relevant history of previous pathologies and surgeries. Disease history includes the histologic types, stage at diagnosis and disease extent at study entry, specific mutations including PD1 expression status and previous antitumor therapy (type, start and end dates, reason for discontinuation and response to the therapy) and smoking history.

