8.2.5 Clinical safety laboratory assessments

See Appendix 2 ([Section 10.2](#)) for the list of clinical laboratory tests to be performed and to the SOA ([Section 1.3](#)) for the timing and frequency. In general, these tests will be done at each cycle; during the first 2 cycles, hematology and liver function tests will be assessed weekly.

If Grade 4 neutropenia occurs, assess ANC every 2 to 3 days until ANC $\geq 0.5 \times 10^9/L$.

In case of Grade ≥ 3 abnormal liver function tests, additional tests will be done every 2 to 3 days until recovery to the baseline value. Additional tests will be performed when clinically appropriate. This test can be performed before the study intervention administration on the same day or the day before.

The Investigator must review the laboratory reports and must document this review in the source documents.

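### Appendix 2 equates a 4-week pregnancy-test interval with every other cycle for both cohorts, but in the triplet cohort every other cycle is 6 weeks

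*Protocol*

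**What the plan says.** Appendix 2 (Protocol Section 10.2) requires pregnancy testing in all women of childbearing potential. For the treatment period it adds that "serum/urine pregnancy tests will be performed at the beginning of the visit every 4 weeks (ie, every 2 cycles/every other cycle". No cohort is named, although the table in the same appendix marks its thyroid tests as applying to the triplet cohort only.

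Cycle length differs between the cohorts. In the doublet flow chart (Section 1.3.1, footnote c), "D1 of Cycle 2 and of each subsequent cycle corresponds to D15 of the previous cycle". In the triplet flow chart (Section 1.3.2, footnote c), "D1 of Cycle 2 and of each subsequent cycle corresponds to D22 of the previous cycle", and the column heading allows "21 (± 3) days from previous infusion".

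Footnote l of the triplet flow chart states the interval in weeks: "A pregnancy test (serum/urine) will be repeated every 4 weeks before IMP administration". The doublet footnote l has the same wording. The Notes column of the triplet pregnancy-test row points the reader back to Section 10.2.

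On precedence, Section 8.2.5 sends the reader to Appendix 2 "for the list of clinical laboratory tests to be performed and to the SOA ([Section 1.3](#)) for the timing and frequency". Section 8 states: "Adherence to the study design requirements, including those specified in the SOA, is essential and required for study conduct".

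**The concern.** Four weeks equals two cycles only when a cycle lasts 14 days. Amendment 02 added a cohort with 21-day cycles. It adapted several other items to that cohort (weekly hematology in the first cycle only, a separate erythropoietin limit, thyroid tests), but this conversion was left unrestricted. For the triplet, one sentence therefore gives two different intervals.

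A triplet site plans its work by infusion visits. Four weeks does not fall on a 3-week infusion grid, so a site looking for a rule stated in cycles will find only the one in Appendix 2, and that rule gives 6 weeks. What is at stake is how late a pregnancy might be found during treatment with a cytotoxic conjugate. Section 8.3.1 makes pregnancy an event of special interest that calls for immediate notification and, in a female participant, for stopping the study drug. Two sites could also test at different intervals and each point to the protocol.

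**Working it through.** **Inputs.** Stated interval: 4 weeks = 28 days (Appendix 2; footnote l of both flow charts). Cycle length: doublet 14 days, triplet 21 days (footnotes c; Synopsis). Dosing window: ±2 days doublet, ±3 days triplet (flow charts; Section 6.6.4). Median treatment duration: 6 months (Synopsis), taken here as 182 days.

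**1. The plan's own conversion.** Interval = number of cycles × cycle length.
- Doublet: 2 × 14 = 28 days = 4 weeks. This reproduces. With the window: 2 × 12 = 24 to 2 × 16 = 32 days.
- Triplet: 2 × 21 = 42 days = 6 weeks. This does not reproduce. With the window: 2 × 18 = 36 to 2 × 24 = 48 days.

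**2. Excess over the stated interval, triplet.** 42 − 28 = 14 days; range 36 − 28 = 8 to 48 − 28 = 20 days. On this reading the first on-treatment test falls at Cycle 3 Day 1, which is 42 days after first dose. It could be 42 + 7 = 49 days after the screening test, which may be done up to 7 days before dosing.

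**3. Four-week dates against the triplet infusion grid, no delays.**
- Infusions in 182 days: days 1, 22, 43, 64, 85, 106, 127, 148, 169 (nine).
- 28-day dates: days 29, 57, 85, 113, 141, 169 (six).
- Distance to the nearest infusion: 7, 7, 0, 7, 7, 0 days.

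The two schedules meet only every 84 days, the least common multiple of 21 and 28. The first 4-week date cannot be an infusion day even with the window: one cycle ends 18 to 24 days after first dose and two cycles end 36 to 48 days after it.

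**4. Testing at every triplet cycle.** 21 days, range 18 to 24, so always within 28 days when no cycle is delayed. A delay of more than 28 − 21 = 7 days exceeds the limit.

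**5. On-treatment tests per woman, triplet, no delays.**

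| Duration | Every cycle | Every 28 days | Every other cycle |
|---|---|---|---|
| 182 days (9 infusions) | 8 | 6 | 4 |
| 364 days (18 infusions, assumed) | 17 | 12 | 8 |

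Every-cycle testing therefore adds 8 − 6 = 2 tests over 182 days and 17 − 12 = 5 over 364 days, compared with 28-day testing.

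**The case against.** The case for leaving the text alone is that the governing interval is clear. Four weeks appears in both flow charts and in Appendix 2, and nowhere does the protocol say 6 weeks. The cycle count is only a parenthesis, and Sections 8 and 8.2.5 put the flow chart first for timing. A site testing every 6 weeks would breach its own flow chart. The consequence is also small. The cohort plans 6 to 12 DLT-evaluable participants, and the number of women of childbearing potential is not stated and may be zero. Entry requires a negative serum test and agreement to contraception, and the end-of-treatment and 90-day tests are untouched.

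Most of this stands, and it sets the severity. It does not make the conversion true: the parenthesis is false for one of the two cohorts it covers, and the triplet row refers the reader to it.

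A reader might go further and infer that triplet footnote l cannot be followed at infusion visits at all. The documents do not support that. The misfit in step 3 arises only if 4 weeks means an exact day. Read as a maximum, the rule is met by a test before every infusion, and the triplet row carries a mark under Cycle 2 onward. The doublet row carries the same mark, so it does not show that every-cycle testing was intended.

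**Conclusion.** The Appendix 2 conversion is wrong as written for the triplet cohort: it gives 42 days (36 to 48) where the protocol states 28. The point is a low-severity internal inconsistency in a safety schedule. The exposure is limited to triplet sites that apply the cycle count in preference to the 4-week figure in their own flow chart. The day counts assume the nominal cycle lengths with only the dosing window around them.

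A reader might also infer that 6-week testing was intended for the triplet. No section states or justifies such an interval, and footnote l says otherwise. Nor does the point reach the trial's results: the DLT assessment, the dose decisions, the response rate and every analysis in the SAP are unaffected.

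**What to change.** In Appendix 2, limit the phrase about every 2 cycles or every other cycle to the doublet cohort. In Appendix 2 and in footnote l of the triplet flow chart, add: *For the triplet cohort, a serum/urine pregnancy test is done before IMP administration at every cycle, and at least every 4 weeks during the treatment period if a cycle is delayed.*

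The second clause is needed. Section 6.6.4 permits cycle delays and foresees some of more than a month, and a test tied only to the infusion would be postponed with it.

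The cost is a text change in two places and, per woman, about 2 more tests over 6 months than strict 28-day testing (5 more over an assumed 12 months), all at existing infusion visits. A long delay adds an occasional urine or serum test between visits. No cohort total can be given, because the number of women of childbearing potential is not stated and participants not evaluable for DLT are replaced. SAP Section 1.1 records that the triplet cohort had not started when SAP version 2.0 was written, so at that point the correction could still have preceded dosing.

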10.3.1 Definition of AE

AE definition

- An AE is any untoward medical occurrence in a patient or clinical study participant, temporally associated with the use of study intervention, whether or not considered related to the study intervention.
- NOTE: An AE can therefore be any unfavorable and unintended sign (including an abnormal laboratory finding), symptom, or disease (new or exacerbated) temporally associated with the use of study intervention.

Events meeting the AE definition

- Any abnormal laboratory test results (hematology, clinical chemistry, or urinalysis) or other safety assessments (eg, ECG, radiological scans, vital signs measurements), including those that worsen from baseline, considered clinically significant in the medical and scientific judgment of the Investigator (ie, not related to progression of underlying disease), eg:
 - Leading to IMP discontinuation or modification of dosing, and/or
 - Fulfilling a seriousness criterion, and/or
 - Defined as an AESI.
- Exacerbation of a chronic or intermittent pre-existing condition including either an increase in frequency and/or intensity of the condition.
- New conditions detected or diagnosed after study intervention administration even though it may have been present before the start of the study.
- Signs, symptoms, or the clinical sequelae of a suspected drug-drug interaction.
- Signs, symptoms, or the clinical sequelae of a suspected overdose of either study intervention or a concomitant medication.
- “Lack of efficacy” or “failure of expected pharmacological action” per se will not be reported as an AE or SAE. Such instances will be captured in the efficacy assessments. However, the signs, symptoms, and/or clinical sequelae resulting from lack of efficacy will be reported as AE or SAE if they fulfil the definition of an AE or SAE.
- The signs, symptoms, and/or clinical sequelae resulting from lack of efficacy will be reported as AE or SAE if they fulfil the definition of an AE or SAE. Also, “lack of efficacy” or “failure of expected pharmacological action” also constitutes an AE or SAE.

Events NOT meeting the AE definition

- Any clinically significant abnormal laboratory findings or other abnormal safety assessments which are associated with the underlying disease, unless judged by the Investigator to be more severe than expected for the participant's condition.
- The disease/disorder being studied or expected progression, signs, or symptoms of the disease/disorder being studied, unless more severe than expected for the participant's condition.
- Medical or surgical procedure (eg, endoscopy, appendectomy): the condition that leads to the procedure is the AE.
- Situations in which an untoward medical occurrence did not occur (social and/or convenience admission to a hospital).
- Anticipated day-to-day fluctuations of pre-existing disease(s) or condition(s) present or detected at the start of the study that do not worsen.

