	
To assess the safety and tolerability of tusamitamab ravidansine in combination with ramucirumabTo assess the durability of the response to treatment with tusamitamab ravidansine in combination with ramucirumabTo assess anti-tumor activity of tusamitamab ravidansine in combination with ramucirumab on progression free survival (PFS) and disease control rate (DCR)To assess the pharmacokinetic (PK) profiles of tusamitamab ravidansine (SAR408701) and ramucirumab when given in combinationTo assess the immunogenicity of tusamitamab ravidansine (SAR408701) when given in combination with ramucirumab	
Incidence of treatment emergent adverse events (TEAEs) and serious adverse events (SAEs) and laboratory abnormalities according to National Cancer Institute (NCI) Common Terminology Criteria for Adverse Events (CTCAE) V5.0Duration of response (DOR), defined as the time from first documented evidence of CR or PR until progressive disease (PD) determined per RECIST v1.1 or death from any cause, whichever occurs firstProgression-free survival, defined as the time from the first investigational medicinal product (IMP) administration to the date of the first documented disease progression or death due to any cause, whichever comes firstDisease control rate (DCR), defined as the percentage of participants who have achieved confirmed CR, confirmed PR or stable disease as per RECIST v1.1Pharmacokinetic parameters of tusamitamab ravidansine (SAR408701) and ramucirumabIncidence of anti-therapeutic antibodies (ATAs) against tusamitamab ravidansine (SAR408701)

Objectives	Endpoints
Tertiary/Exploratory	

• To explore circulating carcinoembryonic antigen (CEA) as a potential biomarker for activity and to evaluate circulating CEA levels at prescreening	
• Circulating CEA at prescreening, screening, and during the treatment period

Abbreviations: ATA=antitherapeutic antibody; BOR=best overall response; CEA=carcinoembryonic antigen; CR=complete response; DLT=dose-limiting toxicity; DCR=disease control rate; DOR=duration of response; IMP=investigational medicinal product; NCI CTCAE= National Cancer Institute Common Terminology Criteria for Adverse Events; NSQ NSCLC=non-squamous, non small-cell lung cancer; PD=progressive disease; PFS=progression-free survival; PK=pharmacokinetic; PR=partial response; RECIST=Response Evaluation Criteria in Solid Tumors.

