10.3.2 Definition of SAE

If an event is not an AE per definition above, then it cannot be an SAE even if serious conditions are met (eg, hospitalization for signs/symptoms of the disease under study, death due to progression of disease).

A SAE is defined as any untoward medical occurrence that, at any dose:

- a) Results in death**
- b) Is life-threatening**

The term “life-threatening” in the definition of “serious” refers to an event in which the participant was at risk of death at the time of the event. It does not refer to an event, which hypothetically might have caused death, if it were more severe.

- c) Requires inpatient hospitalization or prolongation of existing hospitalization**

In general, hospitalization signifies that the participant has been detained (usually involving at least an overnight stay) at the hospital or emergency ward for observation and/or treatment that would not have been appropriate in the physician's office or outpatient setting. Complications that occur during hospitalization are AEs. If a complication prolongs hospitalization or fulfills any other serious criteria, the event is serious. When in doubt as to whether “hospitalization” occurred or was necessary, the AE should be considered serious.

Hospitalization for elective treatment of a pre-existing condition that did not worsen from baseline is not considered an AE.

- d) Results in persistent disability/incapacity**

- The term disability means a substantial disruption of a person's ability to conduct normal life functions.

- This definition is not intended to include experiences of relatively minor medical significance such as uncomplicated headache, nausea, vomiting, diarrhea, influenza, and accidental trauma (eg, sprained ankle) which may interfere with or prevent everyday life functions but do not constitute a substantial disruption.

e) Is a congenital anomaly/birth defect

f) Other situations:

- Medical or scientific judgment should be exercised in deciding whether SAE reporting is appropriate in other situations such as important medical events that may not be immediately life-threatening or result in death or hospitalization but may jeopardize the participant or may require medical or surgical intervention to prevent one of the other outcomes listed in the above definition. These events should usually be considered serious.

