#### **4.7.2 Adverse events**

##### **General common rules for adverse events**

All AEs will be graded according to National Cancer Institute Common Terminology for Adverse Events (NCI-CTCAE version 5.0) and coded to a lower-level term (LLT), preferred term (PT), high-level term (HLT), high-level group term (HLGT), and associated primary system organ class (SOC) using the Medical Dictionary for Regulatory Activities (MedDRA) version currently in effect at Sanofi at the time of database lock.

The AEs will be analyzed in the following 3 categories:

- Pre-treatment AEs: AEs that developed, worsened or became serious during the pre-treatment period.
- Treatment-emergent adverse events (TEAEs): AEs that developed, worsened or became serious during the treatment-emergent period.
- Post-treatment AEs: AEs that developed, worsened or became serious during the post-treatment period.

Similarly, the deaths will be analyzed in the pre-treatment, treatment-emergent, and post-treatment periods.

The primary AE analyses will be on TEAEs. Pre-treatment AEs and post-treatment AEs will be described separately.

An AE with incomplete or missing date/time of onset (occurrence, worsening, or becoming serious) will be classified as a TEAE unless there is definitive information to determine it is a pre-treatment or a post-treatment AE.

If the assessment of the relationship to IMP is missing for an AE, this AE will be assumed as related to IMP. Missing grade will be left as missing.

Multiple occurrences of the same event in the same participant will be counted only once in the tables within a treatment phase, using the maximum (worst) grade by treatment phase. Summaries will be provided for all grades combined and for Grade  $\geq 3$  (including Grade 5). Missing grades, if any, will be included in the “all grades” category.

The AE tables will be sorted as indicated in [Table 8](#).

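### Protocol 10.3.1 gives opposite rules in adjacent bullets on whether lack of efficacy is itself an AE or SAE, and the SAP has no rule for such events once reported

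*Protocol*

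**What the plan says.** Under the events that meet the AE definition, Protocol 10.3.1 has two consecutive bullets on lack of efficacy, or failure of the expected pharmacological action.

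- The first says that it "per se will not be reported as an AE or SAE. Such instances will be captured in the efficacy assessments". It adds that signs, symptoms and sequelae "resulting from lack of efficacy will be reported as AE or SAE if they fulfil the definition of an AE or SAE".
- The second repeats the sentence on signs, symptoms and sequelae, then says that lack of efficacy "also constitutes an AE or SAE".

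Other text bears on the same question:

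- **Protocol 10.3.1, events not meeting the definition:** "The disease/disorder being studied or expected progression, signs, or symptoms of the disease/disorder being studied", unless more severe than expected for the participant.
- **Protocol 8.3.7:** progression of the underlying disease is listed among events that do not qualify as AEs or SAEs and is recorded on its own eCRF page. Any death within 30 days of the last study intervention is nevertheless to be reported as an SAE.
- **Protocol 10.3.2:** "If an event is not an AE per definition above, then it cannot be an SAE even if serious conditions are met". Its examples include death from progression.
- **Protocol Section 3, both cohorts:** a secondary endpoint is "Incidence of treatment emergent adverse events (TEAEs) and serious adverse events (SAEs) and laboratory abnormalities".
- **SAP 4.7.2:** TEAEs are "AEs that developed, worsened or became serious during the treatment-emergent period", counted as participants with at least one event.

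**The concern.** The two bullets agree on signs and symptoms but reverse each other on whether lack of efficacy is itself an event. A site that records it as an AE is following one sentence of the protocol, and a site that does not is following another. Because 10.3.2 makes SAE status depend on the AE definition, the ambiguity carries through to SAEs. The SAP takes reported AEs as they come and gives no instruction on lack-of-efficacy or progression terms outside its summary of fatal AEs.

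At stake is whether some efficacy failures enter a safety endpoint at some sites and not at others. Disease progression is a reason to stop treatment, and the treatment-emergent period runs to 30 days after the last administration (SAP 4.1). A lack-of-efficacy record would therefore often fall inside that period. It could also enter the table of TEAEs leading to permanent full discontinuation (SAP Table 9).

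**Working it through.** The documents state no figure on this point, so the check is a comparison of text followed by simple proportions.

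**Step 1: do the bullets conflict?** Yes. Both are complete sentences in the current text. Neither defers to the other, and no other section says which prevails. The repeated sentence suggests that two alternative template texts were both kept, but that is an inference.

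**Step 2: does other text settle it?** Only in part.

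| Text | What it covers | Effect on the second bullet |
|---|---|---|
| Protocol 10.3.1, exclusion list | Expected progression, unless more severe than expected | Fits the first bullet; does not name lack of efficacy |
| Protocol 8.3.7 | Progression, and death from progression after 30 days | Fits the first bullet; does not name lack of efficacy |
| Protocol 10.3.2 | A non-AE cannot be an SAE; death from progression is an example | Fits the first bullet, but depends on the AE definition in dispute |
| SAP 4.7.2, analysis of deaths | Splits fatal AEs by context of disease progression | No split for non-fatal TEAEs or SAEs |

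Progression reported as progression is thus largely dealt with. An event recorded as lack of efficacy, or progression entered under that label, is not.

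**Step 3: does it reach the endpoint?** Yes, if a site reports it. TEAE and SAE summaries use the all-treated population (SAP 4.7), with no rule on these terms.

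**Step 4: scale.** Incidence is 100 × (participants with at least one event) / n. One participant whose status changes moves it by 100/n points. That is the shift only if the participant has no other qualifying event; otherwise the overall rate does not move. So 100/n is an upper bound per participant.

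- Doublet: n is 30 to 36 planned treated (SAP 1.1). 100/36 = 2.8 points; 100/30 = 3.3 points.
- Triplet: 6 to 12 is the planned DLT-evaluable number (Protocol 9.2.3). Assuming treated equals DLT-evaluable, 100/12 = 8.3 points and 100/6 = 16.7 points. Non-evaluable participants are replaced (Protocol 4.1), so the treated number may be larger and the shift smaller.

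The documents do not give the number of participants affected, so no total can be computed.

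**The case against.** The strongest reply is that the second bullet concerns lack of efficacy, whereas in this disease treatment failure shows mostly as progression, which has more specific rules. Protocol 8.3.7, the exclusion list in 10.3.1 and the examples in 10.3.2 all point the same way. The SAP already separates fatal AEs in the context of progression. The safety analyses are descriptive, and no hypothesis is tested.

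Most of this stands. A reader might infer that TEAE and SAE counts in general turn on which bullet a site follows, because most participants with metastatic disease will eventually progress. The documents do not support that: the specific rules already keep expected progression out, and the documents do not say how many participants would be recorded under the other label. Nor does each such report add a full 1/n, because participants with another event are already counted.

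What does not stand is that these rules cancel the second bullet. None of them names lack of efficacy or failure of pharmacological action, the list in 10.3.1 excludes only expected progression, and the SAP split covers only fatal events. A site recording lack of efficacy would be following the protocol as written.

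**Conclusion.** The contradiction is real and sits in the current text. Its reach is narrow: sites that record lack of efficacy, or progression under that label, on the strength of the second bullet. For each such participant with no other qualifying event, overall incidence moves by at most 2.8 to 3.3 points in the doublet cohort and at most about 8 to 17 points in the triplet. The doublet figure rests on the planned treated number; the triplet figure assumes that treated equals DLT-evaluable. The count of affected participants is unknown. The DLT and ORR derivations are not directly affected. This is an internal inconsistency worth correcting, not evidence that the safety results as a whole are unreliable.

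**What to change.** **Protocol.** Delete the second bullet. Its first sentence only repeats the preceding bullet, so nothing is lost except the conflicting rule, and 10.3.1 then agrees with 8.3.7 and with its own exclusion list. In the same edit, reconcile 8.3.7, under which every death within 30 days of the last study intervention is an SAE, with 10.3.2, under which death from progression cannot be one. Deleting the bullet does not settle that second conflict, which is a separate route into the SAE counts.

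**Analysis.** Deletion does not repair data already collected. In the doublet SAP, list AEs coded to lack of efficacy or disease progression and show TEAE and SAE incidence with and without them. Leave the reported data unchanged. Put the same rule in the triplet cohort's analysis plan, because SAP 1.1 states that this SAP does not cover that cohort. The triplet had not started when SAP v2.0 was written, so a protocol correction made before its first participant would apply to all its data.

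**Cost.** A short protocol change with notice to sites, since it alters a reporting definition, plus one listing and one additional incidence summary per cohort. No new data are needed.
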